8.5.4 BASELINE DESCRIPTIVE STATISTICS

Summary statistics will be used to describe baseline characteristics and other outcomes of interest. Categorical endpoints will be summarized using proportions and frequencies. Continuous endpoints will be summarized using the mean, median, range or standard deviations. Subgroup summarization based on KiT intervention message frequency or other criteria will also be conducted.

8.5.5 PLANNED INTERIM ANALYSES

An interim analysis within the process evaluation is planned to be performed on user engagement and participant satisfaction with the KiT intervention 3 or 6 months after the start of the intervention; timing is contingent on having enough participants enrolled. The interim analysis will be performed by the process evaluation research team, unblinded to the treatment allocation. The results of the interim analysis will be used as feedback information to the research team to make adjustments to the KiT intervention in real-time. These adjustments could be in the form changing the tone of messaging, changing the wording of messages or switching out topics that had the least user engagement, updating or replacing resources or educational content that had the least user engagement or changing the frequency or sequencing of messaging.

8.5.6 TABULATION OF INDIVIDUAL PARTICIPANT DATA

Individual de-identified participant data will be listed by time point of response to every message and resource sent by the KiT intervention and engagement via clicks on resource and educational links. This individual-level data is required to conduct the process evaluation (interim and full-analysis) to determine on an individual and aggregate scale, what messages and resources participants find the most engaging and useful. This participant data will then enable modifications to the KiT intervention in real-time, improving user uptake and effectiveness. All de-identified participant data will be listed in the data table by study ID number and no PHI information will be listed.

9 PARTICIPANT SAFETY

Due to the nature of the KiT intervention, we do not expect adverse or serious adverse events related to the intervention to occur. If a participant texts KiT any messages signalling a crisis situation (see table 4 for list of crisis key words that will be recognized by KiT), support messages will be delivered by KiT, encouraging the participant to reach out to medical professionals and will offer key contact information for appropriate assistance. The LLM chatbot also has instructions to send the same support messages in case any topic related to suicidal ideation is identified in the more natural language conversation. Participants will have the option to pause the KiT messages at any time if they feel that the intervention messages are causing them to feel uncomfortable or distressed until and if they feel ready to resume the messages again. Any elevated harm, discomfort or distress caused by the KiT messages, communicated to the research team by the participant, will be immediately reported to the Principal Investigator, and the Research Ethics Board, and entered the study database as a note to file.

English Safety Testing

We would like to use a new LLM (using GPT-4) chatbot feature to enhance the participant's experience for a more natural conversation. Prior to implementation, we will conduct a safety evaluation and are requesting access to the question data that enrolled participants have asked using the current question and answer feature. Please note, that the LLM chatbot feature will not be turned on until the English safety testing and analysis are completed. To do this safety evaluation, we will ask the patient questions (in addition to synthetically generated questions) to the KiT LLM and have human raters (investigators and

patient partners) to score the answers from 1-5 based on accuracy, safety and a metric known as the global quality score. The validity and reliability of these metrics were established during several rounds of testing with the raters in addition to literature evidence. The LLM chatbot is not a learning model and will only utilize existing resources gathered for the KiT study. Although, since LLMs are stochastic in nature – i.e., may generate different answers to the same question at different times – we will ask each question 3 times. In addition, we want to test the use of LLMs as evaluators of the quality of answers. In order to do this, we will ask an LLM evaluator to also grade the answer to questions based on the aforementioned criteria, and compare this rating to the human raters. If successful, we plan to have the LLM evaluator continuously assess the questions asked by participants for any sensitive information (e.g., pertaining to suicidal ideation) and the quality of answers given, and flag any potentially harmful case for human review during the study.

It should also be noted we have previously assessed a prototype version of the KiT LLM and an LLM Evaluator (using GPT-4 accessed through UHN's Microsoft Azure subscription) on a set of synthetic questions, with promising results. We are in the process of improving these applications based on feedback from this initial assessment. Examples of these updates include stronger language on recommending visits to the emergency department in certain cases and explicit instructions to consider suicidal ideation when flagging potentially sensitive questions. We plan to test updated versions of the KiT and Evaluator LLMs with the questions already asked by participants during the study.

The English safety testing has been completed and the results are below. Once this amendment is approved them the LLM chatbot will be incorporated in Ontario sites.

English safety testing conclusions (please see accompanying PowerPoint presentation in CTO application)

Common questions to all raters (39 participant questions +12 synthetic questions)

- When considering the full set of questions (39 participant, 12 synthetic), the KiT LLM seems to perform well, with high scores in most metrics, particularly Safety.
- Overall the LLM Evaluator seems to act as, or more, conservative than most human raters (the exception being Patient Partner 2, which was slightly more conservative in general).
 - o There is some subjectivity in how clinicians and patient partners perceive the quality of the KiT LLM answers. For example, while PP2 indicated (few) major safety concerns, PP1 did not indicate any safety concerns. No major safety concerns were also indicated by clinicians.
- GQS metric, which is largely a measure of practicality, was scored lower by human raters (although still with high scores. This is not a major concern to us, as Accuracy and specially Safety scores were high, ***indicating the answers are factual and, most importantly, do not do major harm to participants.***

Participant questions – subset of common questions (39 participant questions)

- When only looking at the common subset of participant questions, KiT LLM still maintains scores in the high-end for all metrics.
- Human raters seem to be more conservative than the LLM Evaluator for most metrics, but not by much.
 - o As before, there is some variability between raters. For example, the LLM Evaluator tends to be more conservative than PP1 for all metrics, and slightly less for PP2. Overall scores for all metrics are still high.
- In particular, the LLM Evaluator seems well calibrated for the Safety metric, being as conservative as the human raters in most cases.

- In general, metric scores show promising results by the human raters – again, in particular with the Safety metric.

Participant questions - all questions, inclusion unique ones per rater (45 questions)

- When considering the entire set of participant questions (including unique questions asked to each rater), the conclusions are similar to when considering the common set of participant questions – which is expected, since the common set is a subset of the questions asked in these analyses.

In general, the human raters are slightly more conservative than the LLM Evaluator, but not by much. The LLM Evaluator seems to be well-calibrated for the Safety metric in particular, being close to the human raters in the scoring.

LLM Evaluator (using GPT-4 accessed through UHN's Microsoft Azure subscription)

- Shows to be well-calibrated to flag answers to humans, especially pertaining to Safety.
- Participant answers, will be flagged if they score an Accuracy/GQS score ≥ 3 , and with a Safety score ≥ 2 (any minor or major concerns).
- Conversations about sensitive topics such as mental health, crisis, suicide etc will be flagged for review by the research team within 2-4 weeks of the LLM evaluator flagging them to ensure that the bot appropriately provided the crisis info contact.
- Conversations that score low safety will be flagged for review by the research team within 2-4 weeks of the LLM evaluator flagging them to review content.
- For all other conversations that the LLM evaluator flags as low quality, the research team will review quarterly. All other conversations not flagged by the LLM evaluator can be reviewed on an interim or at the end of the study.
- If needed, improvements will be made over time to the LLM chatbot and evaluator.

French Safety Testing

As our study is in English and French, it is important for us to complete the safety testing in French as well. The French safety testing methods will be similar to the English.

Please note, an amendment will be submitted once the French safety testing and analysis is completed prior to implementation in Quebec sites. Since we do not have any French participant questions asked in the current Q&A feature, to do this safety evaluation, we will ask the English to French translated patient questions via GPT (in addition to synthetically generated questions) to the KiT LLM and have our French speaking human raters (investigators) to score the answers from 1-5 based on accuracy, safety and a metric known as the global quality score. The validity and reliability of these metrics were established during several rounds of testing with the raters in addition to literature evidence. The LLM chatbot is not a learning model and will only utilize existing resources gathered for the KiT study. Although, since LLMs are stochastic in nature – i.e., may generate different answers to the same question at different times – we will ask each question 3 times. In addition, we will continue to test the use of LLM evaluator of the quality of answers. In order to do this, we will ask an LLM evaluator to also grade the answer to questions based on the aforementioned criteria, and compare this rating to the human raters.

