KiT Intervention Technology and Development: the intervention algorithm will be built and managed by our third-party collaborator, Memotext, based in Toronto. Memotext is a digital patient engagement platform that uses health data and analytics to optimize digital communications. Memotext will be designing, developing, deploying and managing our study intervention in partnership with our study collaborators at UHN, the eHealth Innovation team. Memotext will work with SickKids REDCap administrators to ensure that REDCap API (Application Programming Interface) integration is enabled with SickKids REDCap servers in order to deploy chatbot link-outs to REDCap for PREMs and PROMs data collection. Memotext will only be receiving PHI in the form of participant phone number in order to enact registration between participant’s personal mobile devise (via SMS) and the chatbot; every participant will have their own Study ID number and Memotext will not be privy to the patients’ names or any other personal identifying information. During the consent process, participants will be made aware of all the information collected by the intervention, how this information will be used and who will have access to this information (Memotext and members of the research team); participants will be asked to provide their consent to collect this information within the KiT intervention during the e-consent process. Participants with any type of mobile device that is registered to any mobile network will be able to enroll in this study as text-messaging capabilities are universal for all mobile devices. Participants will be informed that only text-messages via SMS will be sent to their phones and will be advised to be connected to a wifi network when they are accessing links provided by KiT and when completing the outcome measures; this is to ensure that the participant does not incur extra out-of-pocket costs for data usage while not connected to a wifi network. Memotext’s system will maintain logs of all outgoing and

incoming messages, and this de-identified data (only linked to Study ID number), will be compiled into a feedback report that will be reviewed and evaluated by the research team on a periodic basis.

LLM Chatbot feature Technology and Development:

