Data collection from KiT algorithm: Data collected from the KiT algorithm via text messages will include responses to text queries including but not limited to: the date of upcoming medical visits in order to send reminders in advance of the appointment date, responses about what educational content participants' would like to receive, and the number of times participants' click on links provided to online resources, and any questions texted from the participant to KiT as part of KiT's Q&A feature. Memotext will store all responses and engagement metrics to/with KiT algorithm on their secure servers in Toronto. All data collected by KiT algorithm will be de-identified; no PHI or personal identifying information will be collected by the KiT algorithm via text. Memotext will routinely monitor and check the data output from the KiT algorithm and will also track user engagement.

Memotext protects personal information by security safeguards appropriate to the sensitivity of information. They are committed to keeping personal information secure, and have appropriate technical, administrative, and physical procedures in place to protect personal information against loss or theft, as well as authorized access, disclosure, copying, use, modification, disposal or destruction. In addition, methods of protection and safeguards include, but are not limited to, locked filing cabinets, restricted access to offices, security clearances, need-to-know access and technological measures including the use of passwords, encryption and firewalls.

Data collection from LLM chatbot: Data collected from the chatbot will include questions asked by participants and responses to questions related to T1D, as well as respective timestamps. Memotext will store all responses and engagement metrics on their secure servers in Toronto. All data collected will be de-identified; no PHI or personal identifying information will be collected by the chatbot. As mentioned, participants will be asked not to share any identifying information during their conversation with the chatbot.

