	Prompting patient with T1D information from a validated bank of resources	KiT: Hi, I wanted to send you some information about government assistance programs for people living with T1D. The Assistive Devices Program (or ADP) is a government program that may support you with the costs of your diabetes devices. It is something that needs to be renewed each year with the support from your physician. To learn more go to [link] or ask your physician about it at your next appointment.
PREMs/PROMs	Storing patient's questions and notes that they want to bring up in their clinic visits	User: #NOTE: Remember to ask doctor about controlling my blood sugars when exercising User: #NOTE: How to apply for ADP User: #NOTE: Mental health resources at clinic?? KiT: Your next appointment is coming up soon, and I wanted to send you the notes you made so you can discuss them with your team: "Remember to ask doctor about controlling my blood sugars when exercising, How to apply for ADP, Mental health resources at clinic??"
PREMs/PROMs	Administering baseline and end of study questionnaire to patient	KiT: Please click on this link to complete the baseline and follow-up (6 months and 12 months) questionnaires for the study [insert REDCap link]

Table 4: Mental health crisis keywords***Standard response message (to be sent after receipt of flagged keyword)***

ONTARIO: “It sounds like you might be going through something difficult right now. If you feel like you are at immediate risk, please call 911. If not, you can always reach out to your healthcare team for support. Or to talk to someone right away, you can text HOME/ PARLER to 686868 anytime, anywhere in Canada to speak with a trained Crisis Responder through the Crisis Text Line.”

- Other Ontario mental health supports: <https://ontario.cmha.ca/provincial-mental-health-supports/>

QUEBEC: “It sounds like you might be going through something difficult right now. If you feel like you are at immediate risk, please call 911 or 811. If not, you can always reach out to your healthcare team for support. Or to talk to someone right away, you can text HOME/ PARLER to 686868 anytime, anywhere in Canada to speak with a trained Crisis Responder through the Crisis Text Line.”

- Other Quebec mental health supports: <https://amiquebec.org/crisis/>

Standard response message (French)

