ONTARIO : « On dirait que tu vis des moments difficiles. Si tu sens que tu es en danger immédiat, appelle le 911. Sinon, tu peux toujours communiquer avec ton équipe de soins de santé pour obtenir du soutien. Pour parler avec quelqu'un tout de suite, tu peux en tout temps texter HOME / PARLER au numéro 686868, peu importe où tu te trouves au Canada. Tu pourras alors parler avec un intervenant en situation de crise formé par l'intermédiaire de Crisis Text Line ».

- Autres ressources de soutien en santé mentale en Ontario : <https://ontario.cmha.ca/fr/soutien-en-sante-mentale-au-niveau-provincial/>

QUÉBEC : « On dirait que tu vis des moments difficiles. Si tu sens que tu es en danger immédiat, appelle le 911 ou le 811. Sinon, tu peux toujours communiquer avec ton équipe de soins de santé pour obtenir du soutien. Pour parler avec quelqu'un tout de suite, tu peux en tout temps texter HOME / PARLER au numéro 686868, peu importe où tu te trouves au Canada. Tu pourras alors parler avec un intervenant en situation de crise formé par l'intermédiaire de Crisis Text Line ».

- Autres ressources de soutien en santé mentale au Québec : <https://amiquebec.org/crisis/>
<https://www.quebec.ca/sante/conseils-et-prevention/sante-mentale/obtenir-aide-en-sante-mentale/ressources-aide-et-soutien-en-sante-mentale>

Mental health crisis keywords (<https://www.stateofmentalhealth.org/lethal-words>)

- Excedrin/aspirin
- 800 mg
- Ibuprofen/ Advil
- Acetaminophen/ Tylenol
- Nightstand
- Vampire
- Railroad
-  (U+1F48A)
-  (U+1F62D)
- Looney
- 11:11
- Kill myself
- Die
- Antifreeze
- Safe
- Tablets/ pills
- Bathtub / bath tub / bath
- Electrocution / electrocute
- Bridge
- Noose / rope
- Syringe / needle
- Suicide / suicidal
- Train
- Midnight
- Cop / police
- Hopeless/ no hope
- No purpose
- Trapped

- Pain
- Burden
- Pills
- Overdose
- Vomit/ throw up/ puke
- Cut/ cutting
- Binge

Mental health crisis keywords (French)

- *Excedrin/aspirine*
- *800 mg*
- *Ibuprofène/ Advil*
- *Acétaminophène/ Tylenol*
- *Table de nuit*
- *Vampire / veines*
- *Rails / tracks / chemin de fer*
-  (U+1F48A)
-  (U+1F62D)
- *Looney*
- *11:11 / 11 h 11 / 11h11*
- *Me tuer / me suicider / finir mes jours / mettre fin / mettre fin à ma vie / en finir / arrêter de souffrir / passer à l'acte / souffrance / souffrances / souffrance / vie / vi / vivre*
- *Seul au monde / seule au monde / solitude*
- *Mourir*
- *Antigel*
- *Sécurité*
- *Comprimés/ pilules / cachets / médicament / médicaments*

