- *Bain / baignoire*
- *Électrocution / électrocuter / électrocuté / électrocutée*
- *Pont*
- *Rhum / rum / fort*
- *Revolver / gun / fusil / arme / arme à feu*
- *Nœud coulant / corde / pendre / pendu / pendue*
- *Seringue / aiguille / seryngue*
- *Suicide / suicidaire / idées suicidaires / pensées suicidaires / idées noires / tendance*
- *Train*
- *Minuit*
- *Policier / police / agent / officier / forces de l'ordre*
- *Désespoir / désespéré / désespérée / sans espoir / pas d'espoir / plus d'espoir / pus d'espoir / vide*
- *Aucun but / sers à rien / sert à rien*
- *Pris / enfermé / emprisonné / emprisonnée / en prison / étouffer / étouffé / étouffée / piège*
- *Douleur / mal*
- *Fardeau / lourd / poids / peser / pèse / épaules*
- *Somnifère / somnifères*
- *Overdose / surdose / surdosage*
- *Vomi / vomissement / vomir / dégueuler / dégueule / gerber / dégobiller*
- *Couper / découper / coupe*
- *Beuverie / binge / brosse / boire / coup / prendre un coup*

KiT – Sample Messages:

Care Navigation

CARE TEAM Your diabetes care team can be made up of a bunch of different healthcare professionals, such as a nurse, endocrinologist, dietician, social worker, and more!

If you're not sure who is a part of your care team, ask your clinic and check out this handy form from Diabetes Canada which lists out all the different healthcare providers who might be:

<https://www.diabetes.ca/DiabetesCanadaWebsite/media/Managing-My-Diabetes/Tools%20and%20Resources/know-your-team.pdf?ext=.pdf>

CONTACTS It's important to know how to contact your diabetes care team outside of appointments in case you have questions or need their support. Do you know if your clinic has an on-call or urgent number that you can reach them at?? Try saving your care team as contacts in your phone 

PRIMARY CARE A family doctor or nurse practitioner is a really important member of your diabetes care team. They might not be an expert in T1D, but they can support you with all kinds of questions - you can go to them for things like mental health, sexual health, and other physical health concerns (stomach aches, rashes, stuff like that).

If you don't have a family doctor or nurse practitioner, Health Care Connect can help you find one:

https://www.ontario.ca/page/find-family-doctor-or-nurse-practitioner?_ga=2.87075160.154570205.1644426680-1166791615.1644426680

Ketones and DKA

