If you're travelling through more than 5 time zones, you'll probably have to adjust your insulin (you'll usually need more if travelling west ← and less if travelling east → so it's a good idea to chat with your doctor about making changes to your medication dosage or schedule before you leave for your trip!)

TRAVELLING To make sure you can enjoy a stress-free trip, pack lots of extra supplies! It's good to have extra glucose meters, batteries, pumps and infusions sets, insulin and syringes (in case your pump malfunctions), and medications on hand, just in case.

You might even want to split your supplies between two bags, in case one gets lost or stolen!

SECURITY Don't worry - people living with T1D are allowed to carry medical supplies (including emergency juice above the liquid limit) with them when travelling through security! Pumps and CGMs should NOT go through an x-ray machine or body scanner, so you can ask to walk through a regular metal detector or get a pat-down instead.

You can get your doctor to provide you with a letter like this one to make the process of getting through security with your diabetes supplies smoother: <https://www.diabete.qc.ca/wp-content/uploads/2019/04/Voyage-lettreMD-Anglaisdocx-5.pdf>

Chatbot Link Appended to the End of Sample Message

Sample Q&A Answer: Thanks for asking! Hopefully this resource about food labels from Diabetes Quebec answers your question mtxt.io/cyhn5t

Appended to end of message: **If you have more questions, ask our KiT Q&A chatbot at mtxt.io/qachat?sid=12312**

Appended to the end of messages not recognized: **Hmm, looks like we don't have a good answer – sorry about that! Try our new KiT Q&A chatbot at mxtt.io/qachat?sid=12312 to see if you can find an answer there!**

Figure 1: Streamlit prototype app interface

KiT - Keeping in Touch

By using this chatbot you are consenting to its use in research. KiT is a bot, not a human. It is not a replacement for direct care. Do not use KiT to communicate urgent questions or treat medical emergencies. If you have a medical emergency call 911 immediately. KiT can make mistakes and is still under development, we recommend checking the sources of information. You should not provide personally identifiable information.

Reset Chat

 Hello, I am KiT. Just so you know, I am not real a person, just a bot. I am here to help with any diabetes questions you may have.

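### If KiT matches crisis keywords literally, the printed English list in Table 4 misses explicit suicidal phrasings that the French list covers

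*Protocol*

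**What the plan says.** Section 9 (Participant Safety) says that a text signalling a crisis will be answered with messages that encourage the participant to seek professional help and give contact details. For what counts as such a text it points to the Appendix: "see table 4 for list of crisis key words that will be recognized by KiT". Table 4 gives the reply and its trigger: "Standard response message (to be sent after receipt of flagged keyword". No other trigger for the SMS channel is described.

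Table 4 prints an English and a French keyword list. The English list includes 'Kill myself', 'Die', 'Suicide / suicidal', 'Noose / rope', 'Overdose', 'Hopeless/ no hope', 'No purpose' and 'Burden', and also broad terms such as 'Safe', 'Train', 'Bridge' and 'Midnight'. The French counterpart of 'Kill myself' begins "Me tuer / me suicider / finir mes jours / mettre fin / mettre fin à ma vie" and goes on to include 'en finir', 'vie' and 'vivre'. The French counterpart of 'Noose / rope' is "Nœud coulant / corde / pendre / pendu / pendue". The French list also has a firearm line, "Revolver / gun / fusil / arme / arme à feu", with no English counterpart in print.

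The Appendix shows what an unrecognised text receives. Under the label "Appended to the end of messages not recognized" stands an apology with a link to the chatbot, without crisis contacts. On later review, section 6.1.1 says that the message logs "will be compiled into a feedback report that will be reviewed and evaluated by the research team on a periodic basis", and section 10.1.6.1 says "Memotext will routinely monitor and check the data output from the KiT algorithm".

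**The concern.** The sponsor's French list treats ending one's life, ending it all, living and hanging as crisis signals. The printed English list does not contain the corresponding phrases. The breadth of the English list suggests a policy of accepting false alarms in order to avoid misses, and leaving out 'end my life' does not fit that policy.

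Under literal matching, the language of the text would decide whether an explicit statement of suicidal intent is answered with crisis contacts. Participants are about 18 years old, and section 9 makes a commitment to them. The point concerns participant safety. It does not touch the endpoints, the sample size or the analysis.

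**Working it through.** The plan gives no figure to reproduce. The check sets the two printed lists side by side and tests short phrases against them.

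**Inputs.** Both Table 4 lists were retyped as printed: 35 English and 38 French bullets, with variants separated by a slash treated as separate keywords and case ignored.

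**Rule tested.** A text triggers the reply if it contains at least one listed keyword. This is an assumption, because the protocol states no rule. Whole-word and substring matching gave the same results for the three English test texts.

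**Side by side.**

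| Meaning | English list | French list |
|---|---|---|
| kill myself | 'Kill myself' | 'me tuer', 'me suicider' |
| end my life / end it all | none | 'mettre fin', 'mettre fin à ma vie', 'en finir', 'vie' |
| don't want to live | none | 'vivre', 'vie' |
| hang myself | 'Noose / rope' only | 'corde', 'pendre', 'pendu', 'pendue' |
| firearm | none printed | 'revolver', 'gun', 'fusil', 'arme' |

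**Results.**
- 'I want to end my life', 'I want to end it all', 'I want to hang myself': 0 of 3 match the English list, and 0 of 3 match both lists pooled. The result therefore does not depend on whether KiT applies the lists separately by language.
- 'Je veux mettre fin à ma vie', 'Je veux en finir', 'Je veux me pendre': 3 of 3 match the French list.
- English controls with 'kill myself', 'die', 'suicidal' and 'overdose': 4 of 4 match.
- 'Ending my life', 'take my life' and 'don't want to live' also match nothing in English. A repair limited to the three test phrases would leave these open.
- 'I want to end my life, I don't feel safe' does trigger, through 'safe'. The gap concerns texts whose only crisis content is one of the missing phrases.

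**Near matches.** On a string similarity scale from 0 to 1, the closest English entries are 'kill myself' for 'hang myself' (0.64), 'needle' for 'end my life' (0.47), and 'pills' and 'Advil' for 'end it all' (0.40). Only loose fuzzy matching, or matching on meaning, would catch these texts.

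**Proposed additions.** With the phrases listed under the fix, each test text above triggers. 'Can I hang out with friends after a low' does not, whereas bare 'hang' would trigger on it.

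**The case against.** **The matching rule is not stated.** Section 9 commits to answering any text that signals a crisis, and mentions Table 4 in a parenthesis without calling it exhaustive. The words 'recognized' and 'flagged keyword' point to keyword triggering but do not rule out variants or synonyms. This stands, and it makes the finding conditional. A reader might infer that KiT will in fact fail to answer these texts. The document does not support that.

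**The text was read from a PDF.** That the bullets 'Kill myself' and 'Noose / rope' print intact shows only that those bullets are complete, not that no separate bullet was lost. The missing firearm line would sit next to the hanging entry, beside another line printed only in French, so a loss at that place is possible. This also stands. Nothing in the text points to a loss, but the source file should be checked first.

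**The test phrases were picked because they are absent.** Any finite list can be beaten in this way, and this one is broad. A reader might take 0 of 3 as a miss rate or as evidence that the list is poor. It is neither. What keeps the point alive is that the benchmark is the sponsor's own French list.

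**There are backstops.** The chatbot, if the participant opens the link and writes again, has instructions to send the same support messages. Section 9 provides for it at Ontario sites once the amendment is approved, and for Quebec only after a further amendment. Section 4.2 lets participants in both provinces choose their language, so an English-language participant in Quebec would lack this route until then. Log review and Memotext's monitoring could reveal missed phrasings later. These backstops reduce the severity, but none puts crisis contacts in the immediate SMS reply. The safety testing described in section 9 covers the chatbot and its evaluator; no test of the SMS keyword list is described.

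**Conclusion.** The point holds in conditional form. If KiT matches Table 4 literally, the printed English list misses explicit suicidal phrasings that the French list covers, and an English SMS with only such a phrase gets no crisis contacts in the immediate reply. In the check, 0 of 3 English phrases matched and 3 of 3 French equivalents did.

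This rests on two assumptions: literal matching, and a printed list that is complete. How many texts would be affected cannot be estimated from the protocol. The missing firearm line is a question for the source file and not an established defect. The change is worth making because it is cheap and serves a safety commitment that the protocol itself makes.

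**What to change.** 1. Check the Table 4 source file for English bullets that are missing from the printed text.
2. Bring the English list level with the French by adding 'end my life / ending my life / take my life', 'end it all', 'don't want to live' and 'hang myself / hanging myself'. Do not add bare 'hang'. Add 'gun / firearm' if the source file also lacks it.
3. Run one shared set of synthetic crisis phrases through the live SMS matcher in English and French, and confirm that each triggers the standard response. Adding known misses and then showing that they match proves little. This test is the substantive step, and it also settles the unstated matching rule.

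The cost is a short table edit, a keyword update at Memotext and a brief test. The downside is a few more supportive messages sent to texts that are not crises. If the matcher already catches these phrases, the test documents it and little effort is lost.
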